## **1.0 PROTOCOL SUMMARY AND/OR SCHEMA**

This prospective trial will examine whether indocyanine green (ICG)-guided intraoperative transdermal lymphography is non-inferior to pre-operative technetium lymphoscintigraphy (TcL) for detecting sentinel lymph nodes (SLN) in pediatric patients with solid tumors. The primary endpoint is the detection rate for TcL-labeled and ICG-labeled SLNs. Secondary outcomes will include safety of ICG, number of positive nodes detected with each modality in each patient, and the sensitivity rate with each modality. The study population will include any patient under the age of 30 years who requires a sentinel lymph node biopsy for a solid tumor. Each patient will undergo both TcL prior to SLN biopsy and intra-operative ICG transdermal lymphography, thereby simultaneously serving as his/her own control. However, the surgeon will be blinded to the TcL results until after the ICG transdermal lymphography results have been recorded, in order to directly evaluate the detection rate of the ICG. Given the estimated sample size of 59 patients and an annual rate of SLN biopsies on patient under 30 years of age of 10 per year at MSK and 17 patients from the two collaborating institutions, this study will take approximately 4 years to complete. (Schematic provided below)

## Patient Flow Chart

- <1% of patients will fail to map with both modalities. In that rare event, the SLN biopsy will be aborted, and the patient will count as a failure of TcL and ICG in the primary objective.

## 2.1 OBJECTIVES AND SCIENTIFIC AIMS

- Primary Objective
  - Show that the SLN detection rate using ICG-guided transdermal lymphography is not inferior to that of TcL in pediatric solid tumors
- Secondary Objectives
  - Safety of ICG injection
  - Compare the total number of ICG+ and TcL+ SLNs harvested in each patient
  - Compare the percent of patients who have a pathologically positive SLN identified with each technique (sensitivity rate)

## 3.0 BACKGROUND AND RATIONALE

Pediatric solid tumors vary greatly in their propensity to spread to regional nodes. After the development of SLN biopsy in melanoma and breast cancer in adults, pediatric surgeons adopted the technique and applied it to multiple tumors including melanoma, Spitz nevi, and soft tissue sarcomas. Technetium lymphoscintigraphy is the gold standard for mapping and identifying SLNs in pediatric patients with solid tumors. Some surgeons also inject blue dye at the site, but its use has decreased because of frequent hypersensitivity reactions (1,2).

The standard procedure for SLN biopsy includes TcL the morning of or day prior to surgery. Mapping of the SLN is accomplished with nuclear medicine scans shortly after local Tc injection; the scans identify which lymph node basin contains the SLN and how many SLNs there are (average 1-2). In the unlikely event (<3%) that mapping fails, the patient is brought back 2-3 weeks later for repeat mapping. Once mapping is confirmed, the patient is taken to the OR, where a gamma probe is used to identify the hottest point (point with the highest gamma count) on the skin overlying the lymph node basin and an incision is made. The gamma probe and blunt dissection are then used to find the hot node and it is then resected. Given the lack of specificity and resolution using the gamma probe this can result in significant time and dissection. All the hot (gamma probe positive) nodes are removed and the procedure is considered complete when the baseline gamma count of the basin is <10% of the gamma count of the hottest node.

While technetium mapping is reliable, it has several disadvantages. First, it exposes a child to a small amount of radiation. Although the radiation dose is within the range of natural background radiation, it adds to the patient's cumulative radiation exposure. Second, while the gamma probes used to identify the SLN intra-operatively are sensitive, they are not specific, have poor resolution, and do not allow for direct visualization during dissection. The inherent error in the probes and the difficulty discerning lymph tissue from the surrounding fat can make it difficult to identify small SLNs. This disadvantage led to the addition of blue dye to the SLN procedure, but its use has been limited by the high risk of hypersensitivity to the dye. Third, the TcL procedure requires several hours to complete, so most patients spend an additional day in the hospital beginning the day prior to the surgery. Last, four injections of technetium must be given around the tumor site without sedation, which can be difficult in the pediatric population.

Recently, fluorescent lymphatic mapping with indocyanine green has been shown to be equivalent to technetium in cervical, uterine, and breast SLN mapping (3-6). One of the first groups of investigators to exploit these attributes of ICG was Memorial Sloan Kettering's Gynecologic Oncology Service. Jewell et al. published an analysis of a patient series in 2014 showing a 95% detection rate for ICG in uterine and cervical cancer SLN biopsy (3). In 2015, Imboden et al. published results of their study comparing ICG to blue dye, which demonstrated bilateral SLN detection rates of 95.5 and 61%, respectively (4). Xiong et al. performed a meta-analysis of ICG SLN data in 2014 and found a pooled detection rate of 96% (5). ICG also allows for direct transcutaneous visualization and transdermal lymphography using near-infrared cameras. Wishart et al. showed a 100% detection rate for ICG transdermal lymphography in early breast cancer SLN biopsy (6). If ICG is shown to be non-inferior to TcL for the mapping and identification of SLNs in pediatric solid tumors, then the pain, radiation exposure, and time expenditure required for TcL could be eliminated.

## 4.1 OVERVIEW OF STUDY DESIGN/INTERVENTION

### 4.2 Design

This is a prospective, multi-institutional clinical trial to evaluate non-inferiority of ICG-guided SLN biopsy compared with the gold standard TcL-guided SLN biopsy in pediatric patients with solid tumors. Each patient will undergo TcL, consistent with the standard of care, but the surgeon will be blinded to the results preoperatively. Intraoperatively, ICG injection and transdermal lymphography will be used to identify the draining nodal basin and the position of the sentinel nodes. ICG transdermal lymphography will be considered successful if SLNs can be visualized on near-infrared imaging. After the transdermal lymphography results have been recorded, the surgeon will be unblinded to the TcL mapping. All ICG-positive and TcL-positive nodes will be removed and complete excision will be confirmed by intra-operative near-infrared imaging and gamma probe evaluation. Thus, in this trial each patient will serve as his/her own control. If TcL fails, no repeat TcL will be performed, the SLN biopsy will be done with ICG alone, and the patient will be recorded as a failure of TcL (i.e. decreasing the detection rate for TcL). If ICG mapping fails, the TcL results will be used to perform SLN biopsy and the patient will be considered a failure of ICG (i.e. decreasing the detection rate for ICG). In the <1% of patients that fail both TcL and ICG, no SLN biopsy will be performed and the patient will be recorded as a failure of both TcL and ICG. These patients will still contribute data to the primary endpoint (i.e. decreasing the detection rate for both modalities) and safety data, but will not contribute to the other secondary aims. Approximately 59 patients will be enrolled over a period of approximately 4 years.

The primary outcome, SLN detection rate, will be compared between ICG-guided transdermal lymphography and TcL to determine non-inferiority of ICG in this clinical application. Secondary outcomes include the safety of ICG in this clinical scenario, comparisons of the total number of excised nodes identified with each detection method in each patients, and the sensitivity rate (percent of patients with a pathologically positive SLN) for each technique.

### 4.3 Intervention

On the day of or the day before the scheduled OR procedure, the patient will undergo TcL, but the surgeon will be blinded to the results preoperatively. On the day of surgery, 4 cc of 1.25 mg/mL ICG will be injected at 4 points directly surrounding the tumor site (1cc per point, depth will vary with position of the tumor) after the patient is under anesthesia. Transdermal lymphography and analysis of all possible draining nodal basins will then be performed using a near-infrared camera in real time. ICG mapping to the SLN takes approximately 5min. If the SLN cannot be identified 20min after ICG injection, it will be considered a failure of ICG, and the TcL results will be used to perform the SLN biopsy. If the ICG does map and a SLN is identified, the transdermal lymphography results will be recorded and the surgeon will be unblinded to the TcL results. All fluorescent lymph nodes will then be resected using the near-infrared camera. After all ICG-positive nodes have been resected, but before closure, gamma probes will be used intraoperatively to ensure all TcL-positive SLNs have been removed. As is standard with TcL SLN biopsy any activity in the nodal bed <10% of the “hottest” node removed will be considered background. This will act as the threshold for all TcL positive nodes being removed. The detection rates for each tracer, ICG and TcL positivity for every node removed, and number of ICG and TcL positive nodes per patient will be recorded. If TcL fails, no repeat TcL will be performed, the SLN biopsy will be done with ICG alone, and the patient will be recorded as a failure of TcL (i.e. decreasing the detection rate for TcL). If ICG mapping fails, the TcL results will be used to perform SLN biopsy and the patient will be considered a failure of ICG (i.e. decreasing the detection rate for ICG). In the <1% of patients that fail both TcL and ICG, no SLN biopsy will be performed and the patient will be recorded as a failure of both TcL and ICG with respect to detection rate. These patients will still contribute data to the primary endpoint (i.e. decreasing the detection rate for both modalities) and safety data, but will not contribute to the other secondary aims.

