### **Secondary objectives**

Safety will be analyzed with descriptive statistics of the number and type of adverse reactions encountered (per CTCAE guidelines).

The number of nodes identified by each technique will be compared using a paired Wilcoxon signed-rank test.

To evaluate sensitivity, the percent of patients in whom a SLN is found to contain tumor on pathology using each technique will be compared with McNemar's test for matched pair data.

Finally, to determine whether the intensity of each node is associated with pathologic positivity, a logistic regression model will be fit with pathologic positivity as the outcome and intensity as the predictor, and robust standard errors will account for correlation among multiple nodes per patient. This will be done separately for ICG and TcL intensity.

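### The two node-level secondary comparisons use nodes removed after unblinding and scored for both tracers, so each technique can be credited with nodes found through the other

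*Combined protocol and SAP*

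**What the plan says.** Sections 4.2 and 4.3 give the same order of events. The surgeon images transdermally with ICG while blinded to TcL. Then, per section 4.3, "the transdermal lymphography results will be recorded and the surgeon will be unblinded to the TcL results"; section 4.2 agrees: "After the transdermal lymphography results have been recorded, the surgeon will be unblinded to the TcL mapping". Resection follows: "All fluorescent lymph nodes will then be resected using the near-infrared camera". Before closure, "gamma probes will be used intraoperatively to ensure all TcL-positive SLNs have been removed". Section 4.2 summarizes the harvest as "All ICG-positive and TcL-positive nodes will be removed and complete excision will be confirmed by intra-operative near-infrared imaging and gamma probe evaluation".

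The data captured are "ICG and TcL positivity for every node removed, and number of ICG and TcL positive nodes per patient will be recorded". If ICG has not mapped by 20 minutes, the patient is an ICG failure and the biopsy proceeds on the TcL result. If TcL fails, it proceeds on ICG.

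Two secondary objectives draw on these nodes. Section 2.1 sets out to "Compare the total number of ICG+ and TcL+ SLNs harvested in each patient", which section 14.0 analyses by a paired Wilcoxon signed-rank test on nodes attributed to each technique. For pathology, section 14.0 says "the percent of patients in whom a SLN is found to contain tumor on pathology using each technique will be compared with McNemar's test". Sections 2.1 and 4.2 call this quantity a sensitivity rate.

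**The concern.** The protocol summary (section 1.0) explains the blinding as a way to assess ICG detection directly. That protection ends when the transdermal result is recorded. Every node entering the two secondary comparisons is removed later, by a surgeon who knows the TcL map and has both instruments available. Nothing in the plan limits a technique's credit to what it showed independently, and nothing asks which modality first led to a node.

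Section 3.0 gives the aim as dispensing with TcL if ICG proves non-inferior. For that decision a reader will want to know what ICG finds by itself, above all among tumor-positive nodes. If the comparisons are reported as nodes identified by each technique, or as sensitivity, they will be read as answering that question, and they do not.

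**Working it through.** **The plan's own figure.** The sample size concerns only the primary endpoint and is not in dispute. With 95% detection for both techniques, independent failures, a 10-point margin, one-sided alpha 0.05 and 80% power, total discordance is 2 × 0.95 × 0.05 = 0.095, and n = 0.095 × (1.645 + 0.842)² / 0.10² = 58.7, which rounds up to 59. The plan's figure reproduces.

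**Which data come from which phase.**

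| Quantity | Source | Surgeon blinded to TcL? |
|---|---|---|
| ICG detection (primary) | Transdermal record | Yes |
| ICG+ and TcL+ node counts (Wilcoxon) | Removed nodes, both tracers scored | No |
| Patients with a tumor-positive SLN by technique (McNemar) | Same nodes, with pathology | No |

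**Routes of cross-credit.**
1. TcL to ICG: a fluorescent node reached because of the TcL map or gamma probe is scored ICG-positive.
2. TcL to ICG after ICG failure: a node removed under TcL guidance that then fluoresces has no crediting rule. At the assumed 95% detection rate about 59 × 0.05 = 3 patients would be ICG failures. Such a patient could be a failure in the primary analysis and a success in both secondary ones.
3. ICG to TcL: fluorescent nodes come out first, under the camera, and are then scored for radioactivity. Section 3.0 itself says gamma probes resolve poorly and that small SLNs are hard to find, so fluorescence may well lead to hot nodes the probe would have missed.

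**Direction.** Let b be the patients whose tumor-positive SLN unaided TcL alone would find and c those whom unaided ICG alone would find. Let r₁ and r₂ be the fractions of b and c that the other technique's help converts to positive on both. The true ICG-minus-TcL difference is (c − b)/59 and the observed one is [c(1 − r₂) − b(1 − r₁)]/59, so the bias is (r₁b − r₂c)/59. Its sign depends on four quantities, none of which the documents give.

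**Size, under assumptions.** Suppose TcL finds every node-positive patient (c = 0), so that only the TcL-to-ICG route operates. Assume 10%, 20% or 30% of 59 patients are node-positive (6, 12 or 18 after rounding) and unaided ICG misses 10% to 30% of them.

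| | Lowest corner (6 × 10%) | Highest corner (18 × 30%) |
|---|---|---|
| Discordant patients, no assistance | 0.6 | 5.4 |
| Half the misses rescued | 0.3 | 2.7 |
| All rescued | 0 | 0 |

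ICG's true share of node-positive patients in this grid is 70% to 90%. It would be observed as 85% to 95% with half rescued and 100% with all rescued.

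**Effect on the test.** With d discordant patients all in one direction, the exact two-sided McNemar p is 2 × 0.5^d. For d = 6, p = 0.031; for d = 5, p = 0.063. Six is the minimum for p < 0.05, and every expected count in the grid is below six.

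**The case against.** The strongest reply is that fluorescence and radioactivity are physical properties of a node. Section 2.1 speaks of harvested nodes and section 4.2 of excised ones, and scoring both tracers on each is a coherent comparison of labelling. That stands. The fault lies in section 14.0's description of the counts as what each technique identified and in the sensitivity label, both of which imply unaided finding.

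Second, sections 4.3 and 9.0 have every possible draining basin surveyed before unblinding, section 4.2 has basin and node position identified at that step, and section 16.1 stores the mapping data. This also stands in part: ICG does not need TcL to choose where to look, and much of the independent record may already exist. But the plan never ties the secondary analyses to it, and the credited nodes come from later open dissection.

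A reader might also infer more than the documents support:
- *That both comparisons favor ICG.* Credit flows both ways, so the net direction is unknown.
- *That the plan counts fluorescent nodes for ICG after a mapping failure.* It is silent; the recording rule merely permits it.
- *That one assisted find typically removes a significant result.* The step from 6 to 5 discordant patients crosses 0.05 because 6 is the smallest count that reaches it. In most of the assumed scenarios the test has little chance of significance with or without assistance.
- *That restricting ICG credit alone would repair this.* With no matching rule for TcL, it would build in a handicap against ICG.

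**Conclusion.** The point holds as a two-way dependence. As written, the Wilcoxon and McNemar comparisons measure tracer labelling among jointly harvested nodes. They cannot show what either technique identifies unaided, and they leave open whether an ICG mapping failure can count as an ICG success. The order of events and the recording rule are explicit in sections 4.2 and 4.3; the absence of a crediting rule is a matter of reading the whole plan.

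The bias cannot be sized, because the documents give no node-positive prevalence, unaided miss rate or rate of assisted finding. The 0.6 to 5.4 discordant patients rest wholly on the assumed ranges and on TcL finding every positive patient.

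A reader might infer that the primary comparison is compromised by the unblinding. The documents do not support that: the ICG call is recorded before the surgeon sees the TcL result. Since only unpowered secondary endpoints are affected, this is a change to consider rather than a condition for the trial.

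**What to change.** **Data capture.** At the blinded step, record the basins and the number of fluorescent foci. Take the same two items from the preoperative TcL scan. For each removed node, record which modality first led to it. This has to be noted at surgery, since it may not be recoverable later.

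**Section 14.0.** Base the two secondary comparisons, or a prespecified sensitivity analysis beside them, on one symmetric rule:
- a node counts for a technique only if it lies in a basin on that technique's own independent record;
- a patient recorded as a mapping failure of a technique counts as zero for that technique.

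Report separately any tracer positivity found only with the other technique's help, and describe the comparison over all harvested nodes as tracer concordance.

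**Cost.** A few form fields, a short addition to section 14.0 and one analysis. Unblinding, resection and the primary endpoint stay as they are. The limitation is that a basin-level rule does not remove assisted finds inside a basin the technique had already mapped. The first-modality field addresses these only in part, because the surgeon knows both maps during dissection.

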## 5.0 THERAPEUTIC/DIAGNOSTIC AGENTS

ICG is an FDA-approved drug for IV, subcutaneous, and topical use. Safety and effectiveness of this agent in pediatric patients have been established (8-10). ICG is currently used at MSK for viability and perfusion analysis in colorectal and plastic surgery as well as SLN identification in gynecologic cancer. It is supplied in a kit with sterile covers for the near-infrared camera and the agent is easily diluted to the goal concentration of 1.25mg/mL prior to injection.

### 6.1 CRITERIA FOR SUBJECT ELIGIBILITY

Describe the characteristics of the patient/subject population.

#### 6.2 6.1 Subject Inclusion Criteria

- Patients <30 years old with an extracolomic solid tumor, diagnosis confirmed at the enrolling institution, requiring SLN biopsy
- Women of childbearing potential must have a negative pregnancy test (urine or blood) pre-operatively as per the standard hospital policy. A woman of childbearing potential is defined as one who is biologically capable of becoming pregnant.

- Patients who are cleared for surgery as noted in Section 8.0

### **6.3 Subject Exclusion Criteria**

- History of reaction to ICG, iodides, or technetium radiocolloid
- Intracoelomic primary tumors or tumors expected to drain to an intracoelomic SLN
- Patients with extensive prior surgery at the primary site or nodal basin expected to affect the lymphatic drainage
- Patients unwilling or unable to sign informed consent
- Women who are pregnant or breast-feeding.

## **7.0 RECRUITMENT PLAN**

Any patient meeting the above criteria who is referred to a surgery clinic at a participating institution will be recruited for the study. The consenting professional will be responsible for explaining the study to the patient and obtaining written informed consent. The clinical research coordinator will be responsible for registering the patient on study. Recruitment of 59 patients is expected to be completed in approximately 4 years.

## **8.0 PRETREATMENT EVALUATION**

All standard pre-operative tests including CBC, coagulation studies, electrolytes, and imaging (determined by the location and attributes of the tumor) will be obtained within the time limits set forth in the participating institution's pre-operative work-up guidelines. No additional tests will be required prior to our intervention.

## **9.0 TREATMENT/INTERVENTION PLAN**

Pre-operative studies as detailed above will be performed in the days leading up to the intervention. The injection of ICG at 4 points directly surrounding the tumor site will take place at the time of operation after the patient is under anesthesia. Transdermal lymphography and analysis all possible draining nodal basins will then be performed for 20min using near-infrared cameras in real time in the operating room. Immediate ICG mapping and detection results will be compared with the pre-operatively obtained TcL and the standard post-operative pathology results. Patients will be monitored intra-operatively for any adverse reaction to ICG and will be specifically asked about adverse events at the time of follow up 1-4 weeks after surgery.

Day w/ respect to operation	Intervention
-45 to -1 (Baseline)	Pre-operative labs and imaging
-1 to 0 (Visit 1)	TcL
0 (Visit 2)	ICG mapping and SLN biopsy
7-28 (Visit 3)	Post-op evaluation and interview for adverse events

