## **10.1 EVALUATION DURING TREATMENT/INTERVENTION**

No additional tests or follow-up over the standard intra-operative and post-operative monitoring will be required in this trial.

The tests included under standard of care are:

- CBC
- Coagulation tests
- Pre-operative technetium lymphoscintigraphy (TcL)

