## 11.0 TOXICITIES/SIDE EFFECTS

COMMON, SOME MAY BE SERIOUS  In 100 people receiving ICG dye, more than 20 and up to 100 may have:  • Mild burning at the injection site lasting up to a few hours • Green or yellowish discoloration at the injection site lasting up to several hours
OCCASIONAL, SOME MAY BE SERIOUS  In 100 people receiving ICG dye from 4 to 20 may have:  • General yellowish skin discoloration lasting up to 24 hours • Orange urine discoloration lasting up to 24 hours
RARE, AND SERIOUS  In 100 people receiving ICG dye 3 or fewer may have:  • Allergic reaction – most are mild with pruritus and hives, but some can be serious with wheezing/bronchospasm and facial edema

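### No structured adverse-event assessment is scheduled between the end of surgery and day 7, so mild ICG effects that end within 24 hours may be under-counted

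*Combined protocol and SAP*

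**What the plan says.** Section 2.1 names "Safety of ICG injection" as a secondary objective. Section 14.0 (Secondary objectives) analyses it descriptively, as counts and types of reactions classified by CTCAE, with no threshold and no test.

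Section 9.0 says how reactions are found. During surgery, "Patients will be monitored intra-operatively for any adverse reaction to ICG". Afterwards, patients "will be specifically asked about adverse events at the time of follow up 1-4 weeks after surgery". The schedule in the same section places this second step at Visit 3, day 7-28, as "Post-op evaluation and interview for adverse events". The entry for Visit 2 (day 0) covers ICG mapping and the biopsy and names no adverse-event assessment.

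Section 10.1 adds: "No additional tests or follow-up over the standard intra-operative and post-operative monitoring will be required in this trial".

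Section 11.0 lists the expected effects by frequency:

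- Common (more than 20 and up to 100 per 100): "Mild burning at the injection site lasting up to a few hours", and local green or yellow discoloration lasting up to several hours.
- Occasional (4 to 20 per 100): general yellowish skin discoloration lasting up to 24 hours, and "Orange urine discoloration lasting up to 24 hours".
- Rare and serious (3 or fewer per 100): allergic reaction, mostly mild, with no duration given.

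**The concern.** The timing of the questions does not match the timing of the events. The four non-allergic effects in Section 11.0 begin and end in the first day, and the only scheduled interview about adverse events comes one to four weeks later. Monitoring in theatre covers only part of the gap. The patient is anesthetised when ICG is injected and cannot report burning, and changes in skin or urine colour may appear or persist after the operation.

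What is at stake is the completeness of a secondary, descriptive safety summary. It matters somewhat more here than it might elsewhere, because Sections 3.0 and 14.0 argue for ICG partly on the ground that technetium needs painful injections without sedation. Burning after waking is the ICG discomfort that a reader would set against that advantage, and it is in the list of common effects. A symptom that nobody recorded in the first day cannot be recovered at the analysis.

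**Working it through.** **1. The plan's one computed figure.** The sample size matters here only as the denominator of the safety counts. With one-sided alpha 0.05, power 80%, both detection rates 95%, margin 10% (Section 14.0) and independent tests, the discordance is 2 × 0.95 × 0.05 = 0.095, and

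n = (1.645 + 0.842)² × 0.095 / 0.10² = 58.7, rounded up to 59.

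The stated 59 is reproduced. The plan does not state the sidedness of alpha; one-sided 0.025 would give 75. Nothing below changes this figure.

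**2. The time gap.** The interview is 7 × 24 = 168 hours to 28 × 24 = 672 hours after the operation. The longest duration listed for the four transient effects is 24 hours. The question therefore comes 168 − 24 = 144 hours (6 days) to 672 − 24 = 648 hours (27 days) after the longest-lasting of them should have ended. This measures elapsed time, not forgetting.

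**3. What each route of capture can see.**

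| Effect (Section 11.0) | Visible or reportable in theatre? | Scheduled assessment in the first 24 h after surgery | Other route |
|---|---|---|---|
| Burning | No, patient anesthetised | None | Recall at day 7-28; routine charting |
| Local discoloration | Yes, if looked for | None | Same |
| General skin discoloration | Only if it appears during surgery | None | Same |
| Urine discoloration | Only if it appears during surgery | None | Same |
| Allergic reaction | Immediate signs, yes | None | SAE reporting if serious; otherwise as above |

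**4. Expected counts with full capture, per listed effect, in 59 patients.**

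- Common: more than 59 × 0.20 = 11.8, up to 59.
- Occasional: 59 × 0.04 = 2.4 to 59 × 0.20 = 11.8.
- Rare: at most 59 × 0.03 = 1.8.

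**5. Sensitivity to incomplete capture.** The documents give no capture rate. The range of 30% to 90% below is an assumption, used only to show how the counts would respond. Expected recorded count = 59 × true rate × capture.

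| True rate | Full capture | 90% | 50% | 30% |
|---|---|---|---|---|
| 20% (floor of common) | 11.8 | 10.6 | 5.9 | 3.5 |
| 4% (floor of occasional) | 2.4 | 2.1 | 1.2 | 0.7 |

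For an effect with a true rate of 4%, the chance of recording at least one case is 1 − 0.96⁵⁹ = 91% with full capture, 1 − 0.98⁵⁹ = 70% at 50% capture and 1 − 0.988⁵⁹ = 51% at 30% capture.

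**The case against.** The strongest reply is that the plan is not blind in this period. Four parts of it deserve an answer.

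- **Monitoring in theatre and SAE reporting.** Section 9.0 watches for any ICG reaction during surgery, which can catch visible local discoloration and immediate allergic signs. Section 17.3 requires SAE reporting from consent to 30 days after the intervention, and participating sites must report to the coordinating center within 3 days of learning of an event. A reaction that prevents complete dosing is a removal criterion (Section 13.0). All of this stands. A reader might infer that serious allergy would be missed, and the documents do not support that. These routes do not reach burning after waking or non-serious colour change.
- **Routine records and forms.** Section 16.1.1 requires physician notes and operative reports as source documents from participating sites, and says that data collection forms exist. The forms are not in the documents, so one cannot say that they lack a day-0 reaction field. What can be said is that the plan's text describes no such field and no extraction from recovery or ward records.
- **Recall may be good.** Nothing limits the interview to recent events, and patients or guardians may remember. A reader might infer that the count will certainly be too low, or that ICG will look safer than it is. The text supports only that it may be. Nor can one say that the informant will often be the parent of a young child: eligibility extends to under 30 years and no age distribution is given.
- **No decision depends on the count.** It is tempting to argue that poor recall would move an effect from the common to the occasional band. That depends on the figures chosen. At a true rate of 25%, any capture below 20/25 = 80% crosses the line, but 90% capture gives 22.5% and does not; at a true rate of 50%, even 50% capture leaves 25%. Neither rate is in the documents, and nothing in the plan turns on the band.

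**Conclusion.** The point holds in a limited form. As written, the plan has no structured assessment of ICG reactions between the end of surgery and day 7, and four listed effects are expected to have ended at least 6 days before anyone is scheduled to ask about them. The descriptive safety count may therefore under-count mild, short-lived effects, burning after waking most clearly. The size of the under-count cannot be derived from the documents, and the capture figures in the working are illustrations, not estimates.

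The conclusion assumes that the unseen forms do not already contain a timed day-0 reaction item. If they do, the remaining task is only to say so in the protocol. Serious allergic reactions, the primary endpoint and the sample size of 59 are outside this point. It is an inexpensive improvement to a secondary objective, not a flaw in the main comparison.

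**What to change.** In Section 9.0 and its schedule, add to Visit 2 (day 0) a short structured ICG-reaction checklist: injection-site burning, local and general skin discoloration, urine discoloration, allergic signs, and a CTCAE grade for each. Existing staff complete it before discharge and from the anesthesia, recovery and ward records. State in Section 14.0 that the safety summary draws on this checklist and on the interview.

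Keep the day 7-28 interview. Ask there about the same items for any part of the first 24 hours after injection that fell after discharge, as well as about later events.

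The cost is a few minutes of staff time per patient, with no added visit, test or patient. Two limits should be acknowledged. Technetium is also injected around the tumor site (Section 3.0), so a local symptom may not be attributable to ICG alone. A call within 24 hours for patients discharged early would improve capture but adds a study contact beyond the standard monitoring in Section 10.1, so it should be optional. The checklist has to be in place before the patients it is meant to cover are treated.
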